12.7.2 Severity of Adverse Events

All AEs will be assessed for severity, using the following general grading scale:

GRADE 1 Mild: Transient or mild discomfort (< 48 hours); no medical intervention/therapy required.

- **GRADE 2** Moderate: Mild to moderate limitation in activity some assistance may be needed; no or minimal medical intervention/therapy required.
- **GRADE 3** Severe: Marked limitation in activity, some assistance usually required; medical intervention/therapy required, hospitalization possible.
- **GRADE 4** Life-threatening: Extreme limitation in activity, significant assistance required; significant medical intervention/therapy required, hospitalization or hospice care probable.

Severity grades for specific safety parameters will be assigned according to the National Institute of Allergy and Infectious Diseases, DMID Adult Toxicity Table (Modified) in Appendix I. For AEs involving a body system or laboratory value not included in the DMID table, the National Cancer Institute Common Terminology Criteria for Adverse Events (NCI CTCAE) Version 4.0 (2009) will be used. When changes in the severity of an AE occur more frequently than once a day, the maximum severity for the experience that day should be noted. If the severity category changes over a number of days, then those changes should be recorded separately (with distinct onset dates).

12.7.3 Relationship Assessment

For each reported AE, the investigator must assess the relationship of the event to the study drug using the following scale:

Unrelated

- Does not follow a known response pattern to the suspect study drug (if response pattern is previously known).
- Can clearly be explained by the known characteristics of the subject's clinical state or other modes of therapy administered to the subject.

Unlikely Related

- The temporal sequence from dosing of the study drug suggests that a relationship is unlikely.
- Follows a response pattern that is unlike that of the suspect study drug (if response pattern is previously known).
- Could be reasonably explained by the subject's clinical state or other modes of therapy administered to the subject.

Possibly Related

- Follows a reasonable temporal sequence from dosing of the study drug.
- May follow a known response pattern to the suspect study drug (if response pattern is previously known).
- Could also be reasonably explained by the subject's clinical state or other modes of therapy administered to the subject.

Probably Related

- Follows a reasonable temporal sequence from dosing of the study drug.
- Could not be reasonably explained by the known characteristics of the subject's clinical state or any other modes of therapy administered to the subject.
- Is confirmed by improvement on stopping or slowing dosing of the study drug, if applicable.

When an assessment is not provided, the event will be treated as Possibly Related for purposes of regulatory reporting.

12.7.4 Action Taken

For each reported AE, the investigator must document the action taken according to the following criteria:

- No action taken
- Non-pharmacologic treatment added
- New drug therapy added
- Discontinued from study
- New or prolonged hospitalization

12.7.5 **Outcome**

For each reported AE, the investigator must document the outcome according to the following criteria:

- Recovered
- Ongoing
- Unknown
- Death

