6.2 Dose Level

Unit doses of rapastinel (GLYX-13), 225 mg/3 mL or 450 mg/3 mL IV, will be administered in a "slow bolus" injection to each subject in an upper extremity vein within approximately 1 to 2 minutes. Investigator will begin treatment based on the dose level (5 mg/kg or 10 mg/kg) to which the subject was assigned during participation in GLYX13-C-202; subjects originally assigned to 5 mg/kg will receive 225 mg/3 mL, and subjects originally assigned to 10 mg/kg will receive 450 mg/3 mL. If subject experiences adverse event(s) that the investigator believes may be associated with rapastinel (GLYX-13), the investigator may decrease dose level from 450 mg to 225 mg. If at any point the patient cannot tolerate the minimum 225 mg unit dose, the patient should be discontinued from the study.

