6.3 Treatment Plan

Following one month at the dose level (subjects who were assigned to placebo during the randomized withdrawal phase of GLYX13-C-202 are eligible to participate and will begin at the dose level to which the subject was assigned during the stabilization phase of GLYX13-C-202) and dose interval to which the subject was assigned during the randomized withdrawal period of GLYX13-C-202, the investigator may continue the same dose level and dose interval, or may change the dose level and dose interval. The investigator will complete a treatment plan that outlines the dose level and dose interval at which rapastinel (GLYX-13) will be administered. The investigator, at the investigator's discretion, may change the treatment plan to alter dose level and/or dose interval based on the subject's depression status.

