8.2 Method of Assigning Subjects to Treatment Groups

Subjects will be assigned initially to the dose level and frequency to which they were assigned during the randomized withdrawal portion of clinical study GLYX13-C-202. Following one month of participation, dose level and dose frequency may be changed by the investigator according to a treatment plan formulated by the investigator at the investigator's discretion.

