11 EFFICACY ASSESSMENTS

12.7 Adverse Events

Subjects should be queried in a non-leading manner, without specific prompting (eg, "How are you feeling?"). The site study staff should assess emerging symptoms of dissociative reaction similar to those caused by other NMDA antagonists including memory impairment, disturbance in time, body or environmental perception, stilted speech, emotional withdrawal, impaired coordination, motor retardation, bizarre reasoning or illusory experiences in any sensory perception, or confused state; such symptoms may be captured as adverse events.

An "adverse event" is any untoward, undesired, unplanned clinical event in the form of signs, symptoms, disease, or laboratory or physiological observations occurring in a human being participating in a clinical study with an investigational product, regardless of causal relationship. A "pre-existing" condition is one that is present before study drug dosing and is reported as part of the subject's medical history. Pre-existing conditions should be reported as an AE only if the frequency, intensity, or character of the pre-existing condition worsens during the course of the study.

Laboratory abnormalities are not considered AEs unless they are associated with clinical signs or symptoms, or require medical intervention. However, a laboratory abnormality (eg, a clinically significant change detected on clinical chemistry, coagulation, hematology, urinalysis) that is independent from the underlying medical condition and that requires medical or surgical intervention, or leads to study drug interruption or discontinuation, must be considered an AE.

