12.7.1 Recording of Adverse Events

Subjects should be instructed to report all AEs to the investigator. AE collection begins at signing of ICF and ends 30 days after last dosing injection. In addition, the investigator should seek to elicit any clinical or objective reactions by specific questioning (eg, "How have you been feeling?") and, as appropriate, by examination. Information on all AEs should be recorded on the eCRF. All clearly related signs, symptoms, and results of diagnostic procedures performed because of an AE should be grouped together and recorded as a single diagnosis. The component parts of the diagnosis may be listed for verification. If the AE is a laboratory abnormality that is part of a clinical condition or syndrome, it should be recorded as the syndrome or diagnosis rather than the individual laboratory abnormality.

To avoid vague, ambiguous, or colloquial expressions, all AEs should be recorded in standard medical terminology on the eCRF and on the medical record rather than in the subject's own words. Each AE will also be described in terms of duration (start and stop date), severity, association with the study drug, action(s) taken, and outcome.

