15.6 Protocol Amendment

If a protocol has been filed with regulatory agencies or submitted to an IRB and requires changes, a protocol amendment must be written. Any changes to the protocol will be made by the sponsor. All amendments will be sent to the IRB on the study sites' behalf. Sites using a local IRB are then responsible for submitting the amendment to their local IRB for approval.

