Investigator will begin treatment based on the dose level (5 mg/kg or 10 mg/kg) to which the subject was assigned during participation in GLYX13-C-202; subjects originally assigned to 5 mg/kg will receive 225 mg/3 mL, and subjects originally assigned to 10 mg/kg will receive 450 mg/3 mL. If subject experiences adverse event(s) (AEs) that the investigator believes may be associated with rapastinel (GLYX-13), the investigator may decrease dose level from 450 mg to 225 mg. If at any point the subject cannot tolerate the minimum 225 mg unit dose, the subject should be discontinued from the study. There are 3 dose groups (despite weekly or biweekly dosing schedule):

- Low dose group consisting of all subjects whose dose level is 225 mg or 5 mg/kg;
- High dose group consisting of all subjects whose dose level is 450 mg or 10 mg/kg;
- Mixed dose group consisting of all subjects who changed dose level between low dose (225 mg or 5 mg/kg) and high dose (450 mg or 10 mg/kg).

At the screening visit, the Structured Clinical Interview for Depression (SCID) will be administered to determine whether any exclusionary conditions have arisen since subject's completion of GLYX13-C-202. The Columbia Suicide Severity Rating Scale (C-SSRS) will be administered. A physical examination will be conducted to ascertain if significant changes have occurred since the subject ended participation in GLYX13-C-202. Blood and urine samples will be obtained for laboratory analysis. Antidepressant agents used since the subject ended participation in GLYX13-C-202 will be recorded.

[figure not shown]
On Week 1 Day 1, subjects will arrive at the investigative site having fasted for at least 10 hours, with water as desired. Each subject's eligibility will be confirmed; then a physical examination will be performed, and blood and urine samples for laboratory analysis will be obtained. Vital signs will be assessed and mass recorded. Electrocardiogram (ECG) will be recorded,

Each subject will then receive an intravenous (IV) dose of rapastinel (GLYX-13) (225 mg or 450 mg unit dose) in a "slow bolus" injection in an upper extremity vein within approximately 1 to 2 minutes. Subjects will be discharged following determination by the investigator that they are medically able to leave. The aforementioned procedures must be repeated within 24 hours before dosing if screening assessments were performed greater than 7 days before study drug dosing.

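### The closed Action Taken list has no entry for dose reduced or dosing interrupted, so adverse events (AEs) leading to these actions cannot be identified or summarised as such.

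*Protocol*

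**What the plan says.** Protocol 12.7.1 requires each AE to be described by several items, among them "association with the study drug, action(s) taken, and outcome". Protocol 12.7.4 then fixes the vocabulary: "For each reported AE, the investigator must document the action taken according to the following criteria". The five entries are no action, a non-drug treatment, a new drug, withdrawal from the study, and new or prolonged hospitalisation.

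Other sections provide for or mention dosing actions:

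- Protocol 6.2, repeated in SAP 2.0, says that for an AE possibly associated with study drug "the investigator may decrease dose level from 450 mg to 225 mg". A subject who cannot tolerate 225 mg is to leave the study.
- Protocol 12.7 says that a laboratory abnormality that is independent of the underlying condition and needs intervention, "or leads to study drug interruption or discontinuation, must be considered an AE".
- Protocol 12.7.3 counts improvement after dosing is stopped or slowed among the criteria for a probable relationship.
- Under Protocol 6.3, "The investigator will complete a treatment plan that outlines the dose level and dose interval", and may alter either one according to depression status.

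SAP 9.1 tabulates all TEAEs by system organ class and preferred term, and by severity and causality. It also covers common TEAEs, serious and fatal events, and TEAEs leading to premature discontinuation of study drug. The listings cover serious events, discontinuations for AEs, and deaths.

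**The concern.** The protocol authorises a specific response to a suspected drug-related AE and then gives the investigator no way to record it in the field meant for that purpose. The visible analysis plan does not fill the gap.

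Long-term safety is the only objective stated in the visible text. Needing a lower dose because of an AE lies between no action and stopping. A subject who did not tolerate 450 mg and carried on at 225 mg would not appear among the discontinuations. In the action field, the subject could look like one for whom nothing had to be done. A reader judging tolerability from the discontinuation table would not see these subjects.

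**Working it through.** The plan states no figure for this point, so the check compares texts, with one piece of arithmetic for the retrospective flag.

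**1. List against permitted or mentioned actions.**

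| Dosing action | Where it appears | Entry in Protocol 12.7.4 |
|---|---|---|
| Reduction, 450 mg to 225 mg | Protocol 6.2; SAP 2.0 | none |
| Interruption of study drug | Protocol 12.7 (mentioned) | none |
| Leaving the study | Protocol 6.2, 10.2 | withdrawal from the study |

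So 0 of 5 entries cover reduction or interruption, and 1 of 5 concerns study treatment at all. With no 'other', an AE handled only by reduction must be entered as no action or left without a code. If a drug was also started, that action can be coded, but the reduction still cannot.

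**2. Visible SAP 9.1 outputs defined by a dosing action.** There is one table and one listing, both for discontinuation. There is none for reduction or interruption.

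**3. Whether another visible summary recovers the link.**

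- Compliance (SAP 7.2) divides doses taken by visits at which drug was prescribed. A reduced dose counts as a full dose, and a visit without a prescription leaves the denominator.
- Duration of exposure (SAP 7.1) does not depend on dose level. Quarterly dose, even if read in milligrams, is summarised overall and carries no reason.
- Weight-adjusted dose (SAP 7.3) is taken at the first unit-dose visit only.
- SAP 2.0 defines a "Mixed dose group consisting of all subjects who changed dose level between low dose" and high dose. It shows that a level changed, in either direction, but not why. Protocol 6.3 also allows changes for depression status.

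These summaries can show that a dose changed. None shows that an AE was the cause.

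**4. What a retrospective flag must avoid.** SAP 7.3 says that subjects in this study first received 5 or 10 mg/kg, and that Amendment 3 brought in 225 or 450 mg unit doses. For a subject of weight w kg:

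- High level: 10w mg becomes 450 mg. This is fewer milligrams whenever w > 450/10 = 45 kg.
- Low level: 5w mg becomes 225 mg. This is fewer milligrams whenever w > 225/5 = 45 kg.

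Any subject above 45 kg who was dosed in both periods therefore receives fewer milligrams at the switch with no AE-driven reduction. A flag based on milligrams would count the switch as a reduction whenever it was the first dosing after onset of a related AE, even at the low level. A flag based on dose level does not, because SAP 2.0 and Protocol Table 2 treat 225 mg as 5 mg/kg and 450 mg as 10 mg/kg.

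**The case against.** The strongest reply is that little is lost. An AE managed by reduction is still recorded with its dates, severity and causality, and it appears in the general TEAE tables. The treatment plan and dosing record show the dose given. The primary endpoint counts subjects with any AE, and the study is purely descriptive. No visible provision promises a table of AEs leading to reduction. All of this stands, and it limits the point to the missing link between an AE and its dosing action.

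Second, the eCRF is not among the documents and may carry a separate field for action with study drug. Parts of SAP section 9 are not shown. This also stands: the missing output is a statement about the visible text. It does not remove the disagreement between Protocol 12.7.4 and 6.2, which can be read directly.

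Third, interruption is weaker ground than reduction. The visible protocol has no rule for interrupting dosing because of an AE, only the mention in 12.7. That is correct, and reduction carries the point.

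A reader might go further in two ways:

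- **That these AEs are not tabulated at all, or that the primary result is compromised.** SAP 9.1 includes them in its overall TEAE tables, so neither follows.
- **That AE rates by dose would be distorted because a reduced subject moves from the high to the mixed group.** The visible SAP 9.1 names no dose columns, and the visible summaries of disposition, baseline, exposure duration and compliance are overall. Protocol 8.2 describes assignment by the preceding study: "Subjects will be assigned initially to the dose level and frequency to which they were assigned". Nothing visible shows AE tables by these groups.

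**Conclusion.** The point holds as an internal inconsistency with a limited consequence for safety reporting. The required list cannot record a response that the protocol permits, nor one that it mentions. Among dosing actions, only discontinuation has a visible output. TEAEs leading to dose reduction or interruption therefore cannot be identified or summarised as such.

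The size is 0 of 5 entries and no visible table or listing. The number of subjects affected cannot be given, because the documents contain no rate of reductions or interruptions. If there are none, the effect is zero. The AE record, the dosing record and the primary count are not affected.

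The conclusion assumes that the eCRF follows Protocol 12.7.4 and that the unseen parts of SAP section 9 add no such output. It should be fixed because safety is the stated purpose and the analysis part of the repair is small.

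**What to change.** 1. Reconcile Protocol 12.7.4 with 6.2 and 12.7. Add 'dose reduced' and 'dosing interrupted' to the Action Taken list and the eCRF, and allow more than one action per AE, as the plural in 12.7.1 already implies. This changes what is recorded, not any dosing rule.
2. Add to SAP 9.1 a table or listing of TEAEs leading to dose reduction or interruption, beside the discontinuation table.
3. For data already collected, specify a flag for candidate reductions: a change of dose level, from 10 mg/kg or 450 mg to 5 mg/kg or 225 mg, at the first dosing after onset of a related AE. Do not use fewer milligrams as the criterion, so that the Amendment 3 switch is not counted. Label the result as inferred, because a change for depression status can coincide with an AE, and a reduction made at a later visit would be missed.

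For the first item, Protocol 15.6 says that "a protocol amendment must be written", with submission to the IRB, and the eCRF must be updated. The SAP's initial version is dated 12/11/2018, about two years after Amendment 3 (23 Nov 2016), so the new codes may come too late for much of the data. The second and third items cost one extra output, programmed from AE and dosing dates where codes are absent.

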12.8 Serious Adverse Events

An SAE is any AE occurring at any dose that results in any of the following outcomes:

Death

"Death" is an outcome and is NOT the AE. In the event of death, the cause of death should be recorded as the AE. The only exception is "sudden death" when the cause is unknown.

• Is a life-threatening experience

Life-threatening AEs include any adverse drug experience, which, in the view of the investigator, places the subject at immediate risk of death from the reaction as it

occurs. It does not include a reaction that, had it occurred in a more serious form, might have caused death.

- Requires inpatient hospitalization or prolongation of existing hospitalization
- Results in a persistent or significant disability/incapacity

Disability is defined as a substantial disruption in a person's ability to conduct normal life functions.

- Results in a congenital anomaly/ birth defect
- Additionally, important medical events that may not result in death, be life-threatening, or require hospitalization may be considered an SAE when, based upon appropriate medical judgment, they may jeopardize the subject and may require medical or surgical intervention to prevent one of the outcomes listed above. Example: allergic bronchospasm requiring intensive treatment in an emergency room or at home.

All SAEs that result in death or are life-threatening, regardless of causal relationship, must be reported to the medical monitor within 24 hours of the site's knowledge of the event. A copy of the initial SAE report must be received within one (1) business day.

All other SAEs or other events reportable to FDA and/or IRB will be forwarded to the medical monitor within one (1) business day.

The SAE report should provide as much of the required information as is available at the time. The following minimum information is required for reporting an SAE: subject identification, reporting source, and an event outcome. Supplemental information may be transmitted using a follow-up report and should not delay the initial report. The Sponsor will contact the investigational site to solicit additional information or to follow up on the event.

If there is any doubt whether the information constitutes an SAE, the information will be treated as an SAE for the purposes of this protocol. Serious adverse event collection will begin after signing the ICF and end 30 days after the last dose.

Serious adverse events will be followed until resolution or return to baseline (when worsening of a pre-existing condition is reported).

All relevant documentation pertaining to the SAE (additional laboratory tests, consultation reports, discharge summaries, postmortem reports, etc.) will be provided by the investigator to the medical monitor in a timely manner.

13 DATA MANAGEMENT

Study data will be entered into eCRFs. Before data analysis, programmed edit checks will be run against the database to check for discrepancies and reasonableness of the data. All issues resulting from the computer-generated checks will be resolved.

14 STATISTICS

14.1 General Considerations

Quantitative assessments will be summarized using descriptive statistics including the mean, standard deviation, median, minimum and maximum values. Changes from baseline will be summarized where appropriate.

Qualitative assessments will be reported as frequencies and percents within each assessment level. Unless specified otherwise, the denominator for percents will the number of subjects in each treatment group. Shift tables may be produced for some assessments and will contain counts of subjects in each cross-classification level of baseline versus post-baseline assessment without percents. Only subjects with a baseline will be included in these tables but a missing category will be permitted for post-baseline values.

The baseline value for a given assessment will be the last non-missing observation collected before administration of study drug.

